Research Protocol Form
Northwestern University Feinberg School of Medicine
Department of Anesthesiology Research Committee

Title: A Randomized Controlled Trial Evaluating the Effect of the Oxytocin Infusion Rate on Fetal Heart Rate Changes and Maternal Fetal Outcomes during the Initiation of Combined Spinal-Epidural Labor Analgesia

Principal Investigator: [name].

Affiliation: Department of Anesthesiology, Department of Obstetrics and Gynecology, Section of Maternal Fetal Medicine; Northwestern University Feinberg School of Medicine

Institution: Northwestern Memorial Hospital

1.0 Research Aims:

.1 Research Questions(s):

11. Is there an association between the rate of oxytocin administration and non-reassuring FHR changes after the initiation of combined spinal- epidural (CSE) analgesia?

.2 Hypotheses: Patients who receive a lower rate of oxytocin administration will have fewer non-reassuring FHR changes.

2.0 Research significance:

Background:

Combined spinal-epidural (CSE) analgesia is a well-accepted technique for labor analgesia. The incidence of fetal heart rate changes after the initiation of neuraxial analgesia has been reported between 3-23% (1,2) and it is controversial whether the risk is increased with a CSE technique compared to an epidural analgesia technique (3). This wide range in reported risk may be due to fluid and oxytocin management prior to and during the initiation of neuraxial analgesia.

There are many factors that contribute to alterations in the fetal heart rate including stage of labor, fetal head compression, cord compression, and uteroplacental insufficiency. Oxytocin is used in labor and delivery to increase the frequency of contractions and augment uterine contractile strength, thereby establishing a regular pattern of labor. However, the administration of exogenous oxytocin in the presence of an uncoordinated labor pattern confers a risk for increase in uterine contraction frequency, resulting in inadequate relaxation periods. This leads to an increase in the basal tone of the uterus, which may lead to a tetanic contraction with risk decreased uteroplacental blood flow and fetal hypoxemia (3,4). Since the introduction of oxytocin for labor induction in 1948, there have been multiple protocols for the administration of oxytocin, both for labor induction, as well as for augmentation of labor. Many institutions use an active management of labor protocol (AMOL) to facilitate labor and delivery through oxytocin management. Use of the AMOL protocol decreases the duration of labor and the Cesarean delivery rate for dystocia (5). The evidence is divided as to the effect of high- versus low-dose oxytocin administration on fetal heart rate abnormalities (6-10). Merrill et al. randomized patients to low- versus high-dose oxytocin for augmentation or induction of labor (9). Oxytocin was decreased or discontinued more commonly in the high-dose group, both for uterine hyperstimulation and FHR abnormalities. In contrast, a study comparing high-dose oxytocin management with standard care found that there were no differences in fetal outcomes or the incidence of fetal distress between groups (10). One of the limitations of the previous studies is that the labor analgesia was not standardized; and consisted of either traditional epidural (high dose) analgesia or

intravenous opioids. Labor analgesia itself has been implicated as a cause of non-reassuring fetal heart rate tracings. The combination of low-dose combined spinal epidural analgesia and the high-/low-dose oxytocin have not been evaluated.

One of the proposed mechanisms for non-reassuring fetal heart tracings after initiation of analgesia is that the pain relief from neuraxial analgesia causes a decrease in catecholamine release by the sympathetic nervous system (5). The subsequent decrease in the circulating epinephrine concentration contributes to an increase in uterine tone, as epinephrine is a potent tocolytic agent. The increased tone, in turn, leads to a decrease in placental blood flow, and eventually fetal bradycardia.

The optimal oxytocin management in the peri-analgesia initiation period in terms of effects on uterine activity, uteroplacental perfusion, and fetal oxygenation, is not known. Anecdotally, some institutions arbitrarily decrease (or do not increase) the oxytocin infusion rate during initiation of analgesia. We hypothesize that decreasing the oxytocin infusion rate immediately before the initiation of CSE analgesia will cause fewer adverse fetal heart rate changes in the first 60 minutes following initiation of labor analgesia compared with maintaining the infusion rate.

3.0 Literature:

4.0 Investigational Plan

.1 Study design: Double blinded randomized, controlled study.

.2 Methods:

.2.1 Size of study groups The primary endpoint is the incidence of non-reassuring fetal heart rate tracings after the placement of CSE. Group sample sizes of 162 in each of two groups 80% power to detect an effect size (W) of 0.1560 using a 1

degree of freedom Chi-Square Test with a significance level (alpha) of 0.05000. The incidence of fetal heart rate changes was estimated based on data from Kinsella, et al (11). The proportion of subjects with adverse fetal heart rate changes in the low-oxytocin and fluid bolus treatment group is estimated to be 8%, Therefore 350 patients will be enrolled to account for patient drop-out or ineligibility.

.2.2 Subject entry, exclusion and dropout criteria: Healthy nulliparous or multiparous women with a term ($37 \geq$ week gestation), singleton pregnancy in spontaneous labor or with spontaneous rupture of membranes, who request neuraxial analgesia, and who receive oxytocin augmentation per institutional protocols, will be eligible to participate in the study. Maternal exclusion criteria will include the presence of any systemic disease (e.g., diabetes mellitus, hypertension, preeclampsia); use of chronic analgesic medications; prior administration of systemic opioid labor analgesia; non-vertex presentation; scheduled induction of labor; or any contraindication to neuraxial analgesia.

.2.3 Protocol specific methods: Eligible women will be asked to participate shortly after admission to the Labor & Delivery Unit at Prentice Women’s Hospital during the routine pre-anesthetic interview. Informed, written consent will be obtained. Randomization based on a computer generated random number table; group assignments will be concealed in sealed, opaque envelopes. At the time of request for labor analgesia, group assignment will be determined by opening an opaque envelope. Patients will be randomized to one of two groups:

Group Assignment		Oxytocin Regimen
A		Routine oxytocin
B		Half-dose oxytocin

Fluid Management:

For patients in Groups A or B, an intravenous bolus of 500 mL LR will be initiated when the patient is positioned for CSE placement by the L & D nurse. The bolus will be administered through a free-flowing wide open intravenous catheter until complete.

Oxytocin Management:

The Prentice Women's Hospital oxytocin augmentation protocols will be used. At the time of request for analgesia, if the patient is in group A the oxytocin management will continue as per the normal oxytocin protocol.

If the patient is randomized to groups B the dose of oxytocin currently being administered will be halved and not increased for the duration of the study period (60 minutes after the initiation of CSE). Care providers other than the Labor & Delivery nurse managing the fluid and oxytocin infusions, will be blinded to group assignment.

Analgesia Management:

All subjects will receive a maintenance infusion of 125 mL lactated Ringers (LR) solution throughout the study period as per Labor and Delivery protocol. Per institutional protocol, all patients will receive a 500 mL bolus of LR solution at the start of the neuraxial procedure ("wide-open rate") via the mainline IV. Labor analgesia will be initiated in the sitting position at the L3-4 or L2-3 interspace with a routine combined spinal-epidural (CSE) technique. The epidural space will be located with the loss of resistance technique and a 27-g x 5-in pencil point spinal needle will be passed through the epidural needle to the subarachnoid space. The intrathecal injection will consist of bupivacaine 2.5 mg and fentanyl 15 µg. A 20 gauge epidural catheter will be threaded and secured 4-5 cm in the epidural space. A test dose of 3 mL lidocaine 1.5% with epinephrine 1:200,000 will be administered through the epidural catheter. The epidural catheter will be

secured and the patient will be positioned in a lateral recumbent position. Patient-controlled epidural analgesia (PCEA) infusion of bupivacaine 0.0625% with fentanyl 1.95 µg/mL will be started at a rate of 8 mL/h with bolus dose = 8 mL, lock-out interval = 10 min and maximum volume = 32 mL/h.

Fetal heart rate monitoring:

Fetal heart rate monitoring and frequency of uterine contractions will be recorded by external tocodynamometry.

Treatment of hypotension:

Any decrease of 10% or greater from baseline in maternal systolic blood pressure after placement of the CSE will be treated by the IV administration of ephedrine or phenylephrine as guided by maternal heart rate, as per standard practice.

Treatment of non-reassuring fetal heart rate changes:

If there are prolonged fetal heart rate decelerations, recurrent late decelerations, severe variable decelerations, or tachysystole, the Prentice Women's Hospital protocol for oxytocin management and intrauterine resuscitation will be followed.

Study completion:

The study is complete after 60 min after the intrathecal injection. After this time, obstetric and anesthesia management, including fluid and oxytocin management, will not be dictated by study protocol.

Fetal heart rate tracing assessment:

Fetal heart rate tracings will be examined for 30 minutes before and 60 minutes after the initiation of analgesia by a perinatologist blinded to study group off-line after delivery. NICHD guidelines (13) will be used to assess FHR patterns. Non-reassuring FHR patterns will be defined as any one or more of the following: minimal or absent variability, late decelerations, and persistent deceleration (see

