Neonatal data: 1- and 5-minute Apgar scores; fetal umbilical cord gases (if taken); birth weight; neonatal sepsis workup or ICU admission.

Fetal heart rate tracing data: see appendix

.2 Data evaluation:

The primary endpoint is the incidence of non-reassuring fetal heart rate tracings during the first 60 minutes after the placement of CSE. Cross tabulation tables will be constructed with the presence or absence of the endpoint as rows and the groups as columns. Differences in the frequency among groups will be assessed using a X^2 statistic. Exact tests will be computed using Monte-Carlo sampling of 10,000 samples with a confidence level of 99%. An interim data analysis will be conducted after completion of the first 175 evaluable participants.

Secondary outcomes and demographics: Age, height, weight, gestational age, fetal station, and frequency of contractions will be compared using ANOVA or Kruskal Wallis ANOVA with post-hoc comparisons correction for multiple comparisons. Binominal and ordinal data will be compared between groups using the X^2 statistic or the Fisher's exact test. A $P < 0.05$ will be required to reject the null hypothesis.

6.0 Interpretation of Anticipated Results:

We anticipate that the lower dose of oxytocin will cause fewer adverse fetal heart rate

changes in the first 60 minutes following initiation of labor analgesia.

7.0 Budget:

- .1 Materials:** No additional materials will be required as all of the materials used in the study are routinely used in the management of patients.
- .2 Labor Requirements:** Existing anesthesia personnel on Labor & Delivery Unit.
- .3 Presentation Cost:** Anticipated presentations at MARC, SOAP and ASA meetings.

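### The primary test ignores the pre-CSE tracing that the plan already has read; stratifying by it would recover power at almost no cost

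*Combined protocol and SAP*

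**What the plan says.** **Planning rate.** 4.0 .2.1 gives 162 per group, 80% power, W = 0.1560, a 1-df chi-square test and alpha 0.05. It states that "The proportion of subjects with adverse fetal heart rate changes in the low-oxytocin and fluid bolus treatment group is estimated to be 8" per cent. The Group A rate is not given. The hypothesis in 1.0 is also about changes: "Patients who receive a lower rate of oxytocin administration will have fewer non-reassuring FHR changes".

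**Endpoint and analysis.** In 5.0 .2, "The primary endpoint is the incidence of non-reassuring fetal heart rate tracings during the first 60 minutes after the placement of CSE". The test is an unadjusted table: "Cross tabulation tables will be constructed with the presence or absence of the endpoint as rows and the groups as columns".

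**What counts.** 4.0 .2.3 (Fetal heart rate tracing assessment) defines a non-reassuring pattern as "any one or more of the following: minimal or absent variability, late decelerations, and persistent deceleration", and refers to the appendix. Nothing in the text supplied requires the pattern to be new or worse than before.

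**Baseline reading.** The same paragraph says that "Fetal heart rate tracings will be examined for 30 minutes before and 60 minutes after the initiation of analgesia", by a blinded perinatologist off-line. 5.0 .2 does not mention the earlier 30 minutes.

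**Entry.** The exclusion list in 4.0 .2.2 ("Maternal exclusion criteria will include the presence of any systemic disease" and further items) has no fetal heart rate criterion. All eligible women receive oxytocin augmentation, and 4.0 .2.4 lists fetal bradycardia among its risks.

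**Timing of the intervention.** The envelope is opened at the request for analgesia, and the Group B rate is halved then (4.0 .2.3), so before CSE is placed.

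**The concern.** The research question is whether a lower oxytocin rate prevents fetal heart rate deterioration after CSE. As written, a woman whose tracing was already non-reassuring, and stays so, is an event in whichever arm she falls. Such events carry little information about the intervention but add to the event count and its variance. The difference between arms shrinks, and so does the power of the plain chi-square.

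Baseline status is probably one of the strongest predictors of the outcome, and a blinded reader is already recording it. Leaving it out of the primary test gives up precision that would otherwise be nearly free. It also leaves open, until the data are seen, whether a continuing pattern counts as an event.

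**Working it through.** **1. Reproduce the plan's figure.** Inputs from 4.0 .2.1: N = 2 × 162 = 324, W = 0.1560, alpha 0.05, 1 df. Noncentrality = N × W² = 324 × 0.156² = 7.885. Power from the noncentral chi-square = 0.802. The stated 80% is correct.

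**2. Implied Group A rate.** W = (pA − pB) / (2√(p̄(1 − p̄))), with p̄ the mean of the two rates. Setting W = 0.156 and pB = 0.08 gives pA = 0.1859, or 18.6%. The risk ratio is 0.08/0.1859 = 0.43.

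**3. Endpoint as written, planning rates taken as new-pattern rates.** Let q be the share of women with a qualifying pattern at baseline (an assumption; not in the documents) and s the share of those patterns that continue, equal in both arms. Then A = qs + (1 − q) × 0.1859 and B = qs + (1 − q) × 0.08.

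| q | s | A | B | W | Power, 162 per group |
|---|---|---|---|---|---|
| 2% | 1 | 0.2022 | 0.0984 | 0.1453 | 0.744 |
| 2% | 0.5 | 0.1922 | 0.0884 | 0.1495 | 0.767 |
| 5% | 1 | 0.2266 | 0.1260 | 0.1320 | 0.662 |
| 5% | 0.5 | 0.2016 | 0.1010 | 0.1404 | 0.715 |
| 10% | 1 | 0.2673 | 0.1720 | 0.1151 | 0.545 |
| 10% | 0.5 | 0.2173 | 0.1220 | 0.1270 | 0.628 |
| 20% | 1 | 0.3487 | 0.2640 | 0.0919 | 0.380 |
| 20% | 0.5 | 0.2487 | 0.1640 | 0.1047 | 0.470 |

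At q = 10% with all persisting, the risk ratio moves from 0.43 to 0.1720/0.2673 = 0.64.

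**4. Stratified test in all randomised women.** In each baseline stratum k, take a_k (events in A), m_k (all events), n_Ak, n_Bk and N_k. The Cochran-Mantel-Haenszel statistic is [Σ(a_k − n_Ak m_k/N_k)]² / Σ[n_Ak n_Bk m_k(N_k − m_k) / (N_k²(N_k − 1))]. Simulated power at q = 10%, 162 per group, new-pattern rates 18.6% and 8%:

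| Persistence A / B | Plain chi-square | Stratified | Baseline-free women only |
|---|---|---|---|
| 100% / 100% | 55% | 77% | 77% |
| 50% / 50% | 63% | 68% | 77% |
| 100% / 70% | 80% | 92% | 77% |
| 100% / 50% | 92% | 97% | 77% |
| 50% / 25% | 85% | 87% | 77% |

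Type I error of the stratified test was 0.048 to 0.050.

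**5. The other reading of the planning rates.** Suppose 18.6% and 8% already include continuing patterns. The plain test then has its stated 80%. Take q = 5%, all persisting. The new-pattern rates are (0.1859 − 0.05)/0.95 = 14.3% and (0.08 − 0.05)/0.95 = 3.2%. All the information lies in the 324 × 0.95 = 307.8 baseline-free women. There W = 0.1115/(2√(0.0873 × 0.9127)) = 0.1975, noncentrality = 307.8 × 0.1975² = 12.0, and power is 93%. With half persisting the gain is smaller: 0.815 to 0.844 by simulation.

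The interim look in 5.0 .2 has no stated rule and is not modelled.

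**The case against.** - **The baseline reading may be used after all.** A reader might infer that it is never used. The documents do not support that: 4.0 .2.3 and 5.0 .1 send the fetal heart rate definition and data to an appendix that is not in the text supplied. What stands is that the endpoint and analysis sentences of 5.0 .2 give it no role.
- **The terms are used loosely.** 4.0 .2.1 names the endpoint as non-reassuring tracings and plans from changes in the same paragraph. *Incidence* could mean new onset, and the 8%, based on a cited fluid-preload study, could be a rate of any pattern after CSE. A reader might infer that the stated 80% power is not delivered. That follows only on one reading of the planning rates; on the other it is delivered (step 5).
- **Equal persistence is an assumption.** Halving the rate may clear existing patterns. At q = 10%, persistence of 100% in A and 70% in B brings the plain test back to 80%. The protocol also acts on some patterns in either arm ("If there are prolonged fetal heart rate decelerations, recurrent late decelerations, severe variable decelerations, or tachysystole"), which argues against full persistence. This stands: the loss could be nil. The stratified test was still ahead in each such case.
- **Bias.** A reader might infer that one arm is favoured. Assignment is randomised and the reader is blinded, so it is not.
- **Restricting to baseline-free women.** This may seem the natural remedy. It drops randomised women and has less power if half-dose clears existing patterns (77% against 80% plain and 92% stratified at 100%/70%). It is better kept as a sensitivity analysis.
- **The gap between envelope and injection.** A pattern arising there and continuing still counts as an event. It arises after assignment, so it cannot safely be used for stratification.

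**Conclusion.** The point holds as a loss of efficiency and a gap in definition, not as bias or an arithmetic error. The plan's 162 per group reproduces (80.2%).

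The size depends on the baseline share, which the documents do not give. With planning rates for new patterns and equal persistence, power is 66% to 72% at a 5% share and 54% to 63% at 10%. Across 2% to 20% it runs from 77% down to 38%. If the planning rates already include continuing patterns, or half-dose clears them more often, the plain test may reach 80%.

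The recommendation does not depend on which case is true: the stratified test had more power than the plain one in every scenario checked and kept its type I error. The change should be made before the data are analysed, but the trial's validity does not turn on it.

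**What to change.** **5.0 .2, primary test.** Use a Cochran-Mantel-Haenszel test in all randomised women, stratified by presence or absence of a non-reassuring pattern at baseline, with a stratified risk difference (A minus B) and 95% CI. Use the exact version if a stratum is sparse: at a 5% share the baseline-positive stratum holds only about 324 × 0.05 = 16 women. Report new-onset events in women free of a pattern at baseline as a sensitivity analysis.

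**4.0 .2.3, baseline.** Define it as the 30 minutes of tracing ending when the envelope is opened. The Group B rate is halved at the request for analgesia, so the 30 minutes before CSE may include time on study treatment.

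**5.0 .1, data form.** Add the time of envelope opening. The list has the time of intrathecal injection but not this.

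**4.0 .2.1, planning rates.** State the assumed Group A rate and its basis (W = 0.1560 with 8% implies 18.6%; authors to confirm). Say whether both rates are for new patterns or for any pattern after CSE.

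**Appendix.** If it already gives the baseline reading a role, reconcile 5.0 .2 with it and cite it there.

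**Cost.** One time field, and an off-line reading that starts 30 minutes before envelope opening instead of 30 minutes before CSE. No extra patients or procedures.

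### The 30-minute tracing before CSE is read but has no visible role in the primary 2×2 test; stratifying on its pre-assignment part is a cheap option whose power gain may be close to zero

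*Combined protocol and SAP*

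**What the plan says.** Section 4.0 .2.3 (Fetal heart rate tracing assessment) has a blinded perinatologist read each tracing off-line: "Fetal heart rate tracings will be examined for 30 minutes before and 60 minutes after the initiation of analgesia". The same paragraph defines the event: "Non-reassuring FHR patterns will be defined as any one or more of the following: minimal or absent variability, late decelerations, and persistent deceleration". It then points to the Appendix for detail, as does section 5.0 .1: "Fetal heart rate tracing data: see appendix". The Appendix is not in the supplied text.

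Section 5.0 .2 fixes the endpoint window: "The primary endpoint is the incidence of non-reassuring fetal heart rate tracings during the first 60 minutes after the placement of CSE". The analysis is a simple table: "Cross tabulation tables will be constructed with the presence or absence of the endpoint as rows and the groups as columns". It is tested by chi-square, and "Exact tests will be computed using Monte-Carlo sampling of 10,000 samples with a confidence level of 99"%. No stratum, covariate, exclusion or change-from-baseline term is mentioned.

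Section 4.0 .2.1 sizes the trial on the same endpoint ("The primary endpoint is the incidence of non-reassuring fetal heart rate tracings after the placement of CSE"), with 162 women per group, W = 0.1560, alpha 0.05 and 80% power. One rate is given: "The proportion of subjects with adverse fetal heart rate changes in the low-oxytocin and fluid bolus treatment group is estimated to be 8"%.

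Under 4.0 .2.3 the envelope is opened when the woman asks for analgesia, so assignment comes before CSE.

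**The concern.** A reading that the trial already plans has no visible part in the comparison it could sharpen. The listed exclusions do not include a non-reassuring tracing before CSE, so women with such a pattern can enter. If the pattern continues after CSE, the visible definition counts it in the same way as one that first appears after CSE. The hypothesis and the anticipated results are worded in terms of heart rate changes.

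Two things are at stake, both modest. If a baseline pattern predicts a post-CSE pattern, stratifying on it removes some noise and recovers some power. Whatever happens to power, the crude table cannot show how many post-CSE events occurred in women who already had a pattern.

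**Working it through.** **1. The plan's own power.** Inputs from 4.0 .2.1: N = 2 × 162 = 324, W = 0.1560, alpha = 0.05, 1 df. Noncentrality = N × W² = 324 × 0.024336 = 7.885. The noncentral chi-square gives power 80.2%. The stated 80% reproduces.

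**2. The implied comparator rate.** With equal groups, W = (|pA − pB| / 2) / √(p̄(1 − p̄)), where p̄ is the mean of the two rates. Setting pB = 0.08 and W = 0.1560 gives pA = 0.186. Check: p̄ = 0.133; 0.053 / √(0.133 × 0.867) = 0.156.

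**3. Assumptions that the documents do not supply.** Let q be the prevalence of a baseline pattern and s its persistence, meaning the chance of a post-CSE event given a baseline pattern. Take 18.6% and 8% as total post-CSE rates, as the endpoint is worded. With s equal in both arms, the rate in women without a baseline pattern is (total − q·s) / (1 − q). At q = 10%, s = 30%: Group A (0.186 − 0.03) / 0.9 = 17.3%; Group B (0.08 − 0.03) / 0.9 = 5.6%.

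**4. Simulated power**, 162 per arm, at least 200,000 trials per setting, Pearson chi-square against Cochran-Mantel-Haenszel (CMH) without continuity correction. Crude power is about 81.5% throughout.

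| Baseline (assumed) | CMH power | Gain, equal persistence (points) | Gain, common treatment odds ratio (points) |
|---|---|---|---|
| Not prognostic | 81% | -0.2 | – |
| q 10%, s 20% | 81.8% | +0.2 to +0.3 | -0.1 |
| q 10%, s 30% | 82.8% | +1.2 | +0.7 |
| q 15%, s 30% | 83.5% | +2.0 | +1.4 |
| q 10%, s 50% | 87.4% | +5.8 | about +5 |

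CMH power is for equal persistence. The last column keeps the same total rates and the same mean persistence but lets treatment act in both strata with one odds ratio.

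A separate run set the baseline-to-outcome odds ratio directly, with prevalence from 5% to 30%. Gains were -0.2 to +1.0 points at odds ratios 1-3, +0.8 to +2.6 at 5, and +2.7 to +9.4 at 10-20.

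**5. Type I error.** In the null settings both tests stay between 4.8% and 5.2%.

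**6. Exact versions**, 25,000 trials per setting, equal persistence. Crude power is 79%. Stratified power is 79% with a non-prognostic baseline at 5% prevalence, 80% at q 10%, s 20%, 81% at 10%, 30%, and 85% at 10%, 50%.

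**7. Share of events in women with a baseline pattern**, q·s / total. At q 5%, s 20%: 0.01 / 0.186 = 5% of Group A events and 0.01 / 0.08 = 13% of Group B events. At q 10%, s 30%: 0.03 / 0.186 = 16% and 0.03 / 0.08 = 38%.

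**8. Size of the baseline-positive stratum.** 324 × 2% ≈ 6 women, × 5% ≈ 16, × 10% ≈ 32.

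**The case against.** The strongest reply is that nothing is broken. An unadjusted chi-square with Monte-Carlo exact tests is a legitimate primary analysis for a randomised trial, and it delivers the power claimed. That stands. A reader might infer that ignoring the baseline biases the comparison or inflates type I error. It does neither, because randomisation protects the crude test.

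The model can also be criticised. Equal persistence means no treatment effect in women with a baseline pattern, which no section supports. It also implies uneven prognostic strength: at q 10%, s 50% the baseline odds ratios are 5.6 in Group A and 29 in Group B. At q 10%, s 10% the baseline is inversely prognostic in Group A (odds ratio 0.46). This criticism stands: with a common odds ratio the modest gains shrink, though the larger ones keep their direction.

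Much may sit in the Appendix. The visible text says that the earlier segment is examined, not that it is coded yes or no. A new-onset rule may exist there. The general sentence in 5.0 .2 on comparing binomial data could also cover a descriptive comparison of baseline patterns. A reader therefore cannot infer that the baseline reading goes unused altogether.

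A stronger reading is that the 8% is a new-onset rate, because 4.0 .2.1 speaks of changes, and that the trial is then underpowered. If so, persisting patterns would dilute the contrast, with crude power from 80% (q 2%, s 10%) down to 47.5% (q 15%, s 85%), and stratifying would not restore 80% once prevalence is 5% or more. But both endpoint statements count post-CSE tracings without a new-onset condition, so the documents do not establish that reading.

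Finally, the planned window is not a clean stratifier, because its last part can fall after assignment. That is correct, and it limits the remedy.

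**Conclusion.** The point holds as an optional refinement. The pre-CSE reading has no visible role in the primary test, and the visible endpoint does not separate persisting from new patterns. The planned test is valid and its power reproduces.

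Under assumed prevalence and persistence, stratifying changes power by about -0.2 to +0.3 points if the baseline is weakly prognostic. The gain is about +1 to +2 points at 10-15% prevalence and 30% persistence (+0.7 to +1.4 with a common treatment odds ratio), and about +5 at 10% and 50%. Gains of up to about 10 points appear only at 85% persistence. That is an upper end and should not be expected, since 4.0 .2.3 sends several of these patterns to intrauterine resuscitation and oxytocin management.

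The interpretive benefit depends less on these assumptions: even where power hardly moves, the share of events in women with a baseline pattern can differ visibly between arms. Confidence is medium, because prevalence, persistence and the Appendix are all unknown.

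**What to change.** If the Appendix already has a new-onset rule, state it in 5.0 .2. If not, pre-specify the following before the interim analysis at 175 evaluable participants:

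1. A CMH test, in exact or Monte-Carlo form to match 5.0 .2, stratified by non-reassuring pattern at baseline (yes or no). Report it with the Mantel-Haenszel risk difference and 95% confidence interval, and with the crude chi-square alongside.
2. A secondary comparison of new-onset patterns among women without a baseline pattern. Stratifying alone cannot tell a persisting pattern from a new one in women who already had a pattern.
3. A baseline defined only on the part of the planned 30-minute reading that precedes envelope opening, with the envelope time recorded. Say how women with no such segment will be handled, and how a pattern that first appears between envelope opening and CSE will be counted.

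The cost is one extra recorded time, a shorter baseline window for some women, yes/no coding of the baseline if the Appendix lacks it, and some wording and analysis. The baseline-positive stratum may be small (about 6 to 32 women at 2-10% prevalence), hence the exact version. If the baseline is not prognostic, about 0.2 points of power are lost. Patient management does not change.
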